6. CCI

7. Immunogenicity analysis sets.

- The immunogenicity analysis set is defined as patients who receive at least 1 dose of study treatment and have at least 1 ADA sample analyzed.

9.2. Statistical Methods and Properties

This study has been designed to establish the Maximum Tolerated Dose (MTD) defined as the dose that yields approximately 27.5% probability of DLT and considers equivalent doses that yield probability of DLT in the interval (Equivalence Interval) 22.5% to 32.5%. The 27.5% target was chosen based on safety considerations and is considered appropriate based on simulations and expert input. The prior distribution of DLT is set as a beta (0.5,0.5) and the threshold probability for early termination and dose exclusion is set to 0.95 as suggested

in the original mTPI method.¹¹ Similarly, doses with an incidence of DLT>32.5% (eg, 4 out of 10) cannot be selected as MTD although is allowed by the mTPI method.

The modified toxicity probability interval (mTPI) design uses a Bayesian statistics framework and a beta/binomial hierarchical model to compute the posterior probability of three dosing intervals that reflect the relative difference between the toxicity rate of each dose level to the target rate ($pT = 0.275$) (See [Appendix 7](#)). If the toxicity rate of the currently used dose level is far smaller than pT , the mTPI will recommend escalating the dose level; if it is close to pT , the mTPI will recommend continuing at the current dose; if it is far greater than pT , the mTPI will recommend de-escalating the dose level. These rules are conceptually similar to those used by the 3+3 design, except the decisions of an mTPI design are based on posterior probabilities calculated under a coherent probability model. Being a model-based design, mTPI automatically and appropriately tailors dose-escalation and de-escalation decisions for different trials with different toxicity parameters. More importantly, all the dose-escalation decisions for a given trial can be pre-calculated under the mTPI design and presented in a two-way table. The decision rules to “dose escalate” (E), “no change in dose” (S), “dose de-escalate” (D) or “dose de-escalate, unacceptable toxicity” (U) are described in [Table 2](#).

Table 6. Dose Escalation Levels for IV Administration

Dose Level	Dose (ng/kg)
1 (Starting Dose)	1.5
2	7.5
3	20
4	50
5	100
6	200
7	300
8	400

* Intermediate doses may be evaluated based on clinical findings (eg, a dose between 20 and 50 ng/kg).

Cohorts of patients could receive doses already tested but a dose that is associated with decision “Dose de-escalate, unacceptable toxicity” cannot be revisited and no more patients should be treated at this dose or higher doses for the remainder of the trial.

The maximum sample size for Part 1 would be N=92 but actual sample size will depend on the underlying dose toxicity profile and variability in actual data realization.

The study will continue accruing until one of the three stopping conditions below is triggered.

The algorithm will stop if any of the following criteria is met:

1. The maximum sample size has been achieved.

2. MTD has been identified with sufficient accuracy: 6 to 12 patients have been accumulated on a dose that is currently estimated to be the MTD; or
3. All doses explored appear to be overly toxic and the MTD cannot be determined.

Due to binomial data variability in small samples, DLTs may be observed in a first cohort(s) by chance even when the true Probability (DLT) is fairly low. This could result in the estimated posterior DLT rate to exceed the targeted 27.5% very early in the trial, triggering an early stop when very few patients (2-4) have been treated. To prevent stopping the trial prematurely in such cases, a step-down option with a lower dose of 1.0 ng/kg is added to the dose grid. This dose will be explored only if a high DLT rate occurs in the first cohort assigned to 1.5 ng/kg, ie, it will not be used as a starting dose and the algorithm will always assign the first cohort of patients to 1.5 ng/kg.

The following table shows the probability of escalating to the next dose level for a range of underlying true DLT rates. For example, for a cohort size of n=3 and for a DLT that occurs in 10% of patients, there is a greater than 90% probability of escalating. Conversely, for a DLT that occurs with a rate of 70%, the probability of escalating is 3%. It is assumed that dose escalation occurs with either 0/3 or 1/6 patients with DLTs.

Probability of Escalating Dose

True underlying DLT rate	10%	20%	30%	40%	50%	60%	70%	80%	90%
Probability of escalating dose	0.91	0.71	0.49	0.31	0.17	0.08	0.03	0.009	0.001

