3.2.1. Evaluation of a Priming Dose

Based on toxicity study results, the evaluation of a priming dose to allow subsequent higher level dose administration may be instituted in this study. In addition, blinatumomab, an approved bispecific agent for the treatment of ALL, has been able to overcome symptoms of cytokine release syndrome (CRS) with the implementation of a priming dose (Topp et al, 2014).²¹ Therefore, this study may implement the evaluation of a priming dose during the escalation phase.

The initial priming dose will be defined to facilitate subsequent dose escalation towards establishing the MTD of a dosing regimen that includes a priming dose. The study aims to determine a MTD for an IV dose regimen that does not include a priming dose, and an independent MTD for an IV dose regimen that includes a priming dose. In addition, the study aims to similarly determine a MTD for PF-06671008 administered subcutaneously that may or may not include a priming dose.

The decision to evaluate a regimen that includes a priming dose may be made by the investigators and sponsor prior to reaching a MTD using the following criteria as guidance:

If a dose level induces symptoms consistent with Grade 3 CRS as defined in [Appendix 8](#) lasting for >24 hours considered not to be due to an infusion related reaction (IRR), allergic reaction, anaphylaxis or other causes in a cohort of 2-4 patients after the initial infusion, an additional 1-4 patients (up to approximately 6 patients overall) will be enrolled at that dose to confirm implementation of a priming dose (Dose Prime) for subsequent cohorts. If an additional confirmed CRS of Grade 3 lasting for >24 hours is observed at that dose, then a lower dose, which has been evaluated in at least 2-4 patients, will be chosen as a priming dose (Dose Prime) for subsequent cohorts. If a Dose Prime is selected, dose escalation will continue to determine the MTD of a dose regimen that includes a priming dose. The evaluation of a Dose Prime may be implemented for both the IV and/or SC routes of administration.

If a dose level induces confirmed CRS of Grade 4 considered not to be due to an IRR, allergic reaction, anaphylaxis or other causes, then a lower dose, which has been evaluated in at least 2-4 patients, will be chosen as a priming dose (Dose Prime) for subsequent cohorts.

[figure not shown]

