In addition, observation of a confirmed CRS event that meets the above qualifications following later infusions (ie, after Cycle 1 Day 1) or CRS events that are approaching the limit of tolerability may prompt the investigators and sponsor to include evaluation of a Dose Prime for subsequent cohorts.

After confirmation of the safety of Dose Prime, the treatment schedule will implement the inclusion of the fixed priming dose as the first dose (C1D1) followed by a second dose (C1D8) that will continue to be escalated in subsequent cohorts following an mTPI method in cohorts of 2-4 patients. After the MTD has been established, the priming dose may potentially be further verified in connection to the established MTD/RP2D, including consideration of more than one priming step, if indicated, using information from all patients who were included in the initial priming dose determination as well as those enrolled in subsequent dosing cohorts.

The primary DLT observation period for cohorts that include Dose Prime will be 21 days following the first dose (C1D1). The dose escalation should a Dose Prime be instituted is depicted in Figure 4.

For cohorts instituting a Dose Prime, there will be a 72 hour observation period between the first dose administered to each of the initial patients enrolled (ie, patients contributing to initial DLT evaluation) at a new dose level. In addition to in-patient observation following the C1D1 dose, patients enrolled in cohorts instituting a Dose Prime must also undergo in-patient observation for at least 24 hours (for cohorts where PF-06671008 will be administered IV) or 48 hours (for cohorts where PF-06671008 will be administered SC) following the C1D8 dose.

Figure 4. Study Schematic Should Dose Prime Be Explored

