3.4. MTD Definition

The estimated MTD is the dose level associated with approximately 27.5% of DLT-evaluable patients experiencing a DLT. The target interval for the DLT rate is (22.5%-32.5%). Due to the discreteness of the dose levels and in the interest of the safety of patients, the estimated MTD is the highest tested dose level with DLT rate ≤ 0.325 in at least 6-12 evaluable patients for DLT. The study aims to determine a MTD for a dose regimen that does not include a priming dose administered IV, and an independent MTD for an IV dose regimen that includes a priming dose. In addition, the study aims to determine a MTD for PF-06671008 administered SC and may also determine an independent MTD for a SC dose regimen that includes a priming dose.

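### As worded, the U exclusion rule in Section 9.2 runs trial-wide, so a U on an unprimed regimen would cap the primed MTD that the protocol calls independent

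*Protocol*

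**What the plan says.** **Exclusion rule.** Section 9.2 of the protocol states that a dose with decision U "cannot be revisited and no more patients should be treated at this dose or higher doses for the remainder of the trial". This is the only text that says how far a U reaches. Appendix 7 marks the current dose as intolerable and stops there. SAP Section 2.2.3 repeats the decision table without the exclusion sentence.

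**MTDs sought.** Section 3.4 aims at an MTD for unprimed IV and at "an independent MTD for an IV dose regimen that includes a priming dose". For SC it adds that the study "may also determine an independent MTD for a SC dose regimen that includes a priming dose". SAP 2.2.2 and 2.2.4 carry the same aims, apart from the SC wording in 2.2.2, which says only that the regimen may or may not be primed.

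**Purpose of priming.** Section 3.2.1 says that "the evaluation of a priming dose to allow subsequent higher level dose administration may be instituted in this study". Once chosen, Dose Prime is given on C1D1, "followed by a second dose (C1D8) that will continue to be escalated in subsequent cohorts".

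**Independence.** Sections 3.1 and 3.2.2 make IV and SC escalation independent of each other. No matching sentence covers primed versus unprimed within a route. Section 3.2.2 and SAP 2.2.3 base each mTPI decision on everyone treated so far at a dose level, again without naming the regimen.

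**The concern.** An MTD that cannot exceed a ceiling set by another regimen's DLTs is not independent of that regimen. If unprimed IV reaches U at some dose, the literal rule forbids giving that dose or any higher one to any later patient, primed or not. Those are the doses that priming is meant to make tolerable.

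The plan then has two bad options. If the sentence is obeyed, a stated aim of Part 1 is cut short by data from a different regimen. If it is read as probably intended, the sponsor assigns primed patients to doses that the protocol says no further patient should receive. This is a patient-protection rule in a first-in-patient study, and its scope should not have to be inferred.

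**Working it through.** **1. Reproduce the U boundary.** Inputs from Section 9.2: Beta(0.5, 0.5) prior, target 0.275, exclusion threshold 0.95. With x DLTs in n patients the posterior is Beta(0.5 + x, 0.5 + n − x), and U applies when P(p > 0.275) > 0.95.

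- 2/2: 0.985; 3/3: 0.996; 3/4: 0.977; 4/4: 0.999. All are U.
- 2/3: 0.928; 2/4: 0.845. Neither is U.

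This matches Table 2 and Appendix 7 for cohorts of 2 to 4.

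**2. Can the same events start priming and produce a U?** Section 3.2.1 selects a lower dose as Dose Prime after one confirmed Grade 4 CRS ("If a dose level induces confirmed CRS of Grade 4 considered not to be due to an IRR", or to the other listed causes). Section 3.3 counts Grade 3 or higher CRS as a DLT unless it was not maximally treated, or was maximally treated and fell to Grade 2 or lower within 72 hours. Two Grade 4 CRS events in a cohort of 2, both maximally treated and unresolved at 72 hours, are therefore 2/2 DLTs, which is U. So the answer is yes. Often, however, priming will start without a U, because CRS that resolves in time is not a DLT.

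**3. What the literal rule would close (illustration only).** Table 1 lists 1.5, 7.5, 20, 50, 100, 200, 300 and 400 ng/kg. Assume Dose Prime is 50 and unprimed IV reaches U at 100. The legend to SAP Figure 2 places primed dose levels above Dose Prime.

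- Literal rule: 100, 200, 300 and 400 are closed. No listed level above Dose Prime remains. Only an intermediate dose between 50 and 100 is open, for example 50 × 1.67 = 83.5 ng/kg if the 67% cap that follows a first DLT applies.
- Per-regimen rule: none of those four levels is closed to primed IV by the unprimed result, although the cap may mean that they are approached in smaller steps.

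Counts of listed levels do not measure impact. Section 3.2.2 allows intermediate doses and caps increases after the first DLT, and the documents do not say whether that cap carries over into primed escalation.

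**4. Is a U a realistic event? (background only)** For a first cohort the chance is p² for n = 2, p³ for n = 3, and 4p³(1 − p) + p⁴ for n = 4.

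| Assumed true DLT rate | n = 2 | n = 3 | n = 4 |
|---|---|---|---|
| 27.5% | 7.6% | 2.1% | 6.6% |
| 40% | 16.0% | 6.4% | 17.9% |

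These are chances of a U at one dose. They are not the frequency of the conflict, which also depends on the unprimed toxicity curve and on when priming starts. The documents give neither.

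**5. Which scope does the context favour?** Section 9.2 also says "The study will continue accruing until one of the three stopping conditions below is triggered", and one of those conditions is that an MTD has been found. A study seeking several MTDs cannot stop at the first. It says further that "the algorithm will always assign the first cohort of patients to 1.5 ng/kg", yet SC escalation starts at the IV Dose Prime level. Table 10 in Appendix 7 sets its maximum of 50 patients per regimen, against 92 for Part 1 overall. Section 9.2 therefore reads as a description of a single mTPI run, and its reference to the trial probably means that run.

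**The case against.** The strongest reply is that no informed reader would apply the rule across regimens. The primed MTD is called independent. Section 3.2.1 says escalation continues once Dose Prime is selected. The SAP figure legend gives the primed regimen its own ladder, and Section 9.2 uses trial in the generic sense of the mTPI literature. Appendix 7 says its simulations begin after the priming dose is chosen, on the basis of lower-grade, non-DLT cytokine release. Its grade wording differs from Section 3.2.1, but it suggests that priming was expected before any U. All of this stands as evidence of intent. None of it limits the sentence, and the independence text that does exist covers only route.

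A reader might infer that site staff would be dosing patients at forbidden levels on their own judgment. Section 5.1 does not support that: the sponsor specifies dose and route and gives written permission for each patient. The exposure is an ambiguous rule applied by its author and visible to sites and ethics committees.

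The worked route to a U is narrow. The minimum 72-hour gap between the first doses of initial patients makes a second severe CRS event less likely, though it does not exclude one. That stands too.

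Finally, the literal reading is the cautious one, in a study without an external data safety monitoring committee (Section 9.7). The caution is legitimate, but a blanket bar defeats a stated aim. The risk it guards against can be handled by targeted review.

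**Conclusion.** The conflict in the text is real: an explicit exclusion rule without a regimen limit contradicts the stated independent primed MTD, for IV and, where pursued, for SC. Its weight is low to moderate, and it is worth correcting at the next amendment.

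It rests on two conditions: that a U occurs on the unprimed regimen before or during primed escalation, and that Section 9.2 is applied as written. Its frequency cannot be computed.

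A reader might go further and conclude that the sponsor intends a cross-regimen ceiling, that the design cannot deliver a primed MTD, or that most of the dose range would be lost. The documents support none of these. Context points to a per-regimen intent, priming can begin without any U, and intermediate doses below the closed level stay available. Nor is a cap of SC by an IV result a serious reading, because Section 3.2.2 lets the two routes escalate independently.

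**What to change.** - **Protocol 9.2:** replace the closing words that extend the bar to the whole trial with: for the remainder of escalation in that regimen (route and priming status).
- **Protocol 3.2.2 and SAP 2.2.3:** say that decisions use patients at the same dose level of the same regimen.
- **Protocol 3.2.1:** keep the bar on using a U dose as Dose Prime. The C1D1 priming dose is itself given to an unprimed patient, so the unprimed result applies to it directly.
- **Protocol 9.2:** require sponsor and investigator review before a primed cohort reaches a dose that was closed in the unprimed regimen because of non-CRS DLTs.

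The cost is a few clauses. The edit changes a dose-exclusion rule, so it needs a protocol amendment with IRB/EC approval (Section 12.1) and a matching SAP edit. Table 2, the sample size and the simulations do not change. The downside is that primed patients may receive, from C1D8, a dose closed in the unprimed regimen. The review step limits that risk where the toxicity was not CRS.

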9.3. Sample Size Determination

This first in patient study is divided in to two parts. Up to approximately 152 patients are expected to be enrolled in the study overall.

In Part 1, patients will participate in a dose escalation phase aimed at estimating the MTD. The sample size for this component of the study will vary depending on the number of DLTs observed. It is anticipated that the maximum sample size of approximately 92 patients are expected to be enrolled in Part 1 of the study at approximately 6 sites. The actual number of patients enrolled will depend upon tolerability and the number of dose levels required to identify the MTD.

The minimum and maximum sample sizes after which Part 1 can be stopped and MTD declared are approximately 6-12 and approximately 92 patients, respectively. As for the number of patients treated at each dose, it is expected that the typical number will be 1 to 4 patients for the doses actually studied. However, since variable cohort size is allowed, the actual number of patients treated at each dose will vary from 1 to 12.

In Part 2 the maximum sample sizes for each tumor indication (ie, TNBC, CRC and NSCLC) will be in the range n=10 to n=20. Enrollment of patients in one indication may be discontinued if minimal or no anti-tumor activity (eg 0 or 1 response) is observed in the first 10 evaluable patients for that indication. Assuming a non-informative prior (ie, Jeffrey's prior) if 1 out of 10 patients have tumor response, this would predict a posterior probability

(Beta-Binomial) equal to 0.93 that the true response is inferior to 30%. On the other hand, if 7 out of 20 patients have tumor response, this would predict a posterior probability equal to 0.70 that the true response is not inferior to 30% and a posterior probability equal to 0.05 (5%) that the true response is inferior to 20%. In addition, posterior probabilities may be calculated by using informative priors based on the antitumor activity that may be observed during Part 1 (eg 2 out of 3 TNBC patients experience tumor response in Part 1). These posterior probabilities will be assessed for each indication during Part 2 when at least the first 10 Pts are enrolled in that indication. Posterior Probabilities >0.75 of an ORR<20% (eg, 0,1 out of 10; 0,1,2 out of 16) may provide evidence of no substantial anti-tumor activity for that indication.

Assuming a Kappa statistic equal to 0.7, N=20 would determine a 90% CI lower bound equal to 0.44 if Kappa is calculated as a measure of concordance between positive/negative P-cadherin results in different samples when the proportion of P-cadherin positive is 80%.

9.4. Efficacy Analysis

In this First In Patient study anti-tumor activity is a primary objective for Part 2 of the study.

Tumor response will be presented in the form of patient data listings that include, but are not limited to, tumor type, starting dose, tumor response at each visit, and best overall response. In addition, progression date, death date, date of first response and last tumor assessment date, and date of last contact will be listed.

The definition of each response category is provided in [Appendix 4](#) (RECIST v1.1) CCI

9.5. Analysis of Pharmacokinetics CCI

9.5.1. Analysis of Pharmacokinetics

PK parameters for single dose including the maximum concentration (C_{max}), time to maximum concentration (T_{max}), and area under the concentration versus time curve (AUC_{last} , $AUC_{sd,\tau}$) will be estimated using non-compartmental analysis. PK parameters for multiple dose (assuming steady state is achieved) including the maximum concentration ($C_{ss,max}$), time to maximum concentration ($T_{ss,max}$), and area under the concentration versus time curve ($AUC_{ss,\tau}$) will be estimated using non-compartmental analysis. If data permit or if considered appropriate, area under the concentration versus time curve to infinity (AUC_{inf}), terminal elimination half-life ($t_{1/2}$), clearance (CL) for IV administration or apparent clearance (CL/F) for SC administration, volume of distribution at steady state (V_{ss}) for IV administration or apparent volume of distribution at steady state (V_{ss}/F) for SC administration, and accumulation ratio ($R_{ac} = AUC_{ss,\tau}/AUC_{sd,\tau}$) will be also estimated. Actual sample collection times will be used for the parameter calculations. The PK parameters will be summarized descriptively by dose, cycle, dosing day and route of administration.

PF-06671008 concentrations will be summarized descriptively (n, mean, SD, coefficient of variation(CV), median, minimum, maximum, geometric mean and its associated CV) by dose, cycle, day and nominal time. Median profiles of the concentration-time data will be plotted by dose, cycle and day (single dose and steady state) using nominal times, for dosing intervals with full PK profile. Median profiles will be presented on both linear-linear and log-linear scales.

Dose normalized AUC_{inf} (AUC_{τ} at steady state), AUC_{last} and C_{max} will be plotted against dose (using a logarithmic scale) by cycle and dosing day. These plots will include individual patient values and the geometric means for each dose level. These plots will be used to help understand the relationship between the PK parameters and dose.

The observed accumulation ratio and the linearity ratio will be summarized descriptively. Each will be analyzed after natural log transformation using a one-way analysis of variance with a single term for dose. The means and 90% confidence intervals (CIs) obtained from the model will be back-transformed to provide means and 90% CIs for the accumulation and linearity ratios for each dose.

Trough concentrations will be plotted for the first 2 cycles using a box-whisker plot by cycle and day within cycle in order to assess the attainment of steady state.

